9.2.2.1 SAE Reporting Requirements to Vergent

The procedure for reporting SAEs, regardless of causal relationship, is as follows:

- Within 24 hours of the Investigator’s knowledge of an SAE, the site must notify Vergent by phone call to their site monitor, medical monitor or other Vergent representative. They should also immediately complete the AE eCRF and select “Serious”.
- The initial reporting of an SAE should contain as much information as is available to the Investigator. Submission of the SAE via the EDC should not be delayed in order to collect additional information to complete the form.
- When available, de-identified hospital records, autopsy reports, and other documents should be sent to the Vergent Safety Mailbox: [contact].
- The Investigator is responsible for reporting their site SAEs to their IRB/HREC according to site specific procedures. The CRA will follow-up at monitoring visits to ensure each SAE for the site has been submitted to their IRB/HREC per their site-specific requirements and the information will be routinely tracked by the CRA in their monitoring visit report.
- If a related SAE or SUSAR is reported at any site, Vergent will distribute the report to every site involved in the study for distribution to their IRB/HREC.
- The Investigator must take all therapeutic measures necessary for resolution of the SAE. Any medications necessary for treatment of the SAE must be recorded onto the concomitant medication section of the subject’s eCRF.

9.2.3 Clinical Laboratory Abnormalities

Laboratory abnormalities are usually not recorded as AEs unless considered to be clinically significant by the site clinician. In this study “clinically significant” is defined as an abnormality that induces clinical signs or symptoms, if the abnormality is of a degree that requires active management (e.g., discontinuation of the study drug, dose modification) or when the event is requiring treatment or other therapeutic intervention (e.g., potassium supplements, blood transfusion, etc.).

The Investigator will evaluate the relationship of any significantly abnormal result to protocol treatment or clinical condition, if possible. All clinically significant abnormal laboratory results will be followed until they return to normal or become stabilized.

9.2.3.1 Evaluation of Key Clinical Laboratory Values Post-Baseline:

[illegible]

9.2.4 Pregnancy Reporting

Pregnancy is not considered an AE. Nevertheless, any pregnancy that occurs between dosing and as evaluated in the End-of-Study Visit (Days 25 – 35), should be verified and recorded. Sites should complete the Pregnancy Form provided by Vergent, and submit it to the Vergent Safety Mailbox ([contact]) within 24 hours of knowledge. Subjects or their female partner will sign a separate consent form allowing the Study Site and Sponsor to follow up with them through 6 weeks post-delivery or termination of the pregnancy.

10. STATISTICS

The study analyses will be conducted in a GCP environment (ICH E6). All analyses will be pre-specified in a Statistical Analysis (SAP) and finalized prior to database lock. If the methods in the SAP do not agree with this protocol, the methods described in the SAP will govern the analysis.

Additional post-hoc statistical tests may be performed and will be further described in the SAP.

Quantitative data will be presented as a standard set of summary statistics (n, mean, standard deviation, median, minimum and maximum values). Categorical data will be expressed as frequency (%).

10.1 Sample Size Determination

10.2 Populations for Analysis

The study includes three prospectively defined study populations.

1. The Safety Population includes any subject who received any amount of VGT-309.
2. The Intent to Treat (ITT) Population will include all patients who received any amount of VGT-309 and had surgery with NIR imaging after the surgeon first attempts to locate the tumor/nodule by white light palpation.
3. The Evaluable Population (EP) will include the subset of ITT patients who were eligible, who had no major protocol deviations, who received at least 90% the prescribed amount of VGT-309, and the surgeon first attempted to locate the tumor/nodule by adequate white light and/or palpation followed by adequate NIR imaging.

10.3 Hypothesis Tests

10.3.1 Treatment Comparisons

There is only one treatment in this unblinded single-arm study. The hypothesis to be tested is not a treatment comparison. The hypothesis to be tested is that the lower bound of a 95% confidence interval for the observed proportion of subjects with at least one CSE exceeds 10%.

10.3.2 Primary Hypothesis

The primary study hypothesis is that VGT-309 with NIR imaging is superior to white light and/or palpation for the intraoperative localization of preoperatively identified lung lesions.

The null hypothesis for the primary endpoint is that $\leq 10\%$ of subjects will have at least one CSE, while the alternative hypothesis is that proportion of subjects with at least one CSE will exceeds 10% as demonstrated by at least 15/86 (17.4%) evaluable subjects with at least one CSE.

For the primary endpoint analysis, the proportion of subjects with at least 1 CSE will be tested under the null hypothesis that this proportion is $\leq 10\%$.

$$H_0: p \leq 10\%$$

The alternative hypothesis states that the proportion of evaluable subjects with at least 1 CSE will be greater than 10%:

$$H_a: p > 10\%$$

The primary analysis will use the EP population. This analysis may be repeated using the ITT population. One-sided 2.5% exact binomial test will be used to test the null hypothesis. Clopper-Pearson exact two-sided 95% confidence intervals will be reported.

For the secondary endpoint analysis sensitivity, PPV, and 1-PPV will be calculated and presented along with 95% confidence intervals using GEE model analysis to factor in within-subject correlation for subjects with multiple tumors.

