Statistical Methods	
Sample Size:
 
For the primary efficacy endpoint of proportion of subjects with at least one CSE, assuming a 20% true rate of at least one CSE, two-sided 5% Type 1 error and 80% power, the sample size to rule out a CSE rate less than or equal to 10% requires 86 evaluable subjects in the primary analysis group. The trial will have met the primary endpoint if at least 15/86 (17.4%) subjects have at least one CSE. The 95% two-sided Clopper-Pearson exact confidence bound at 17.4% is (10.1%, 27.1%).
 
Efficacy
 
A descriptive analysis of the baseline subject and tumor characteristics will be performed. Quantitative data will be presented as a standard set of summary statistics (n/mean (standard deviation)/median/minimum/maximum). Categorical data will be expressed as frequency (%).
 
For the primary endpoint analysis, the proportion of subjects undergoing NIR imaging with at least 1 CSE will be identified and tested under the following null hypothesis:
 
Ho: $P \leq 0.10$
 
The alternative hypothesis states that the proportion of subjects undergoing NIR imaging with at least 1 CSE will be greater than the chosen margin of 0.10:
 
Ha: $P > 0.10$
 
At 86 evaluable subjects, this trial is power at 80% to reject the null hypothesis of a 10% or fewer of subjects experiencing at least one CSE. Two-sided 95% exact confidence intervals for the proportion of subjects with at least one CSE will be constructed.
 
For the secondary endpoint analysis sensitivity, PPV, and 1-PPV will be calculated and presented along with 95% confidence intervals using GEE model analysis to factor in within-subject correlation for subjects with multiple tumors.
 
Safety:
 
Adverse event (AE) data will be listed by subject. Treatment-emergent adverse events (TEAEs), serious adverse events (SAEs), and AEs leading to study drug discontinuation will be summarized by system organ class and preferred term using the current version of the Medical Dictionary for Regulatory Activities (MedDRA).
 
Listings of individual subject laboratory results will be provided. Laboratory results, Clinically Significant and change from baseline for selected lab tests will be summarized by treatment at scheduled visits.
 
Twelve-lead ECGs and vital signs measurements will be listed by subject and summarized by incidence of events/abnormalities or descriptive statistics as appropriate. Individual data for physical examination findings, prior and concomitant medications and medical history will be provided.

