2. STUDY OBJECTIVE AND ENDPOINTS

2.1 Objectives:

2.1.1 Primary Efficacy Objective:

Assess the efficacy of VGT-309 with near-infrared (NIR) imaging for lesion visualization when compared to standard surgical techniques in subjects undergoing surgery for proven or suspected cancer in the lung.

2.1.2 Secondary Efficacy Objective:

Assess the utility of VGT-309 with NIR imaging to identify cancerous tissue as confirmed by histopathology.

2.1.3 Safety Objective:

Determine the safety and tolerability of VGT-309 in subjects with proven or suspected cancer in the lung.

2.2 Endpoints:

2.2.1 Primary Efficacy Endpoint:

Identify the proportion of subjects with at least one Clinically Significant Event (CSE) as defined by:

- A. Intraoperative localization of one or more preoperatively identified lung lesions using VGT-309 with NIR imaging when standard surgical techniques using white light and/or palpation failed to identify the lesion(s), and lesion(s) are confirmed by histologic examination to be other than normal lung tissue.
- B. Identification of one or more synchronous or occult lung lesions using VGT-309 with NIR imaging when standard surgical techniques using white light and/or palpation and preoperative imaging failed to identify the lesion(s), and lesion(s) are confirmed by histologic examination to be cancerous or precancerous.
- C. Identification of fluorescence within ≤ 10 mm from the inside edge of the closest staple line as measured by the investigator *ex vivo* in the operating room using NIR imaging, with pathologic margin confirmed by histologic examination to be ≤ 10 mm.
NOTE: Margins from excisions of known or suspected metastases at the time of the surgery, OR diagnostic wedge resections where a completion lobectomy or segmentectomy was subsequently performed, will not be considered for Margin CSE inclusion.
- D. Identification of lymph nodes by VGT-309 with NIR imaging confirmed by histologic examination to be cancerous.

2.2.2 Secondary Efficacy Endpoints:

To evaluate the sensitivity, positive predictive value (PPV), and 1-PPV of VGT-309 with NIR imaging for lesion(s) *in vivo*:

- 1. Sensitivity is defined as the probability that the tissue fluoresces when it is cancer, as confirmed by histology $(TP/(TP+FN))$ *
- 2. Positive predictive value (PPV) is defined as the probability that a tissue sample contains cancer on histologic exam if it fluoresces $((TP/(TP+FP))$ *

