8.3 Intra-operative Evaluations

During the surgery, the Surgeon/Investigator will first utilize standard surgical techniques using white light and/or palpation followed by *in situ* NIR fluorescence imaging using an NIR imaging system capable of detecting ICG for localization of the primary tumor and any potential synchronous or occult lesions and lymph nodes.

The number and location of pulmonary nodules and synchronous lesions that are visualized by standard techniques and/or by VGT-309 NIR fluorescence imaging will be recorded. Lymph nodes visualized by VGT-309 NIR fluorescence imaging will be identified and recorded by nodal station and zone.

Following extraction of any tumor/nodules, synchronous lesions, and lymph nodes, *ex vivo* NIR fluorescence imaging will take place in the operative suite prior to closing the surgical field.

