## 9.2. Statistical Hypothesis for the Primary Efficacy Endpoint

The primary study hypothesis is that VGT-309 with NIR imaging is superior to white light and palpation for the intraoperative localization of preoperatively identified lung lesions. The null hypothesis for the primary endpoint is that  $\leq 10\%$  of subjects will have at least one CSE, while the alternative hypothesis is that proportion of subjects with at least one CSE will exceed 10%.

For the primary endpoint analysis, the proportion of subjects with at least 1 CSE will be tested under the null hypothesis that this proportion is  $\leq 10\%$ .

$$H_0: p \leq 0.10$$

The alternative hypothesis states that the proportion of evaluable subjects with at least 1 CSE will be greater than 10%:

$$H_a: p > 0.10$$

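### The primary hypothesis says NIR imaging is superior to standard technique, but the test can show only that NIR used after standard technique adds events in more than 10% of subjects

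*Protocol*

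**What the plan says.** **The claim.** Protocol 10.3.2 gives the primary hypothesis as "VGT-309 with NIR imaging is superior to white light and/or palpation for the intraoperative localization of preoperatively identified lung lesions". SAP 9.2 has "The primary study hypothesis is that VGT-309 with NIR imaging is superior to white light and palpation", for the same task. The primary objective (Protocol 2.1.1, SAP 2.1) is also worded as a comparison with standard surgical techniques.

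**The test.** Protocol 10.3.2: "One-sided 2.5% exact binomial test will be used to test the null hypothesis". The null is that at most 10% of subjects have a CSE. The synopsis gives the rule: "The trial will have met the primary endpoint if at least 15/86 (17.4%) subjects have at least one CSE". SAP 9.3 specifies the same test. Protocol 10.3.1 says that the hypothesis tested is not a treatment comparison. The readable SAP does not repeat that statement, and Protocol 10 lets the SAP govern where the two differ.

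**The events.** Of the four CSE types in Protocol 2.2.1, only type A (item 1 in SAP 3.1 and 9.1) concerns preoperatively identified lesions. It requires that white light and/or palpation failed, that NIR succeeded, and that histology shows something other than normal lung.

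**Order and data.** Under Protocol 8.3 the surgeon uses standard technique first and NIR second. Number and location are recorded for lesions "visualized by standard techniques and/or by VGT-309 NIR fluorescence imaging will be recorded".

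**Secondary endpoints.** In vivo sensitivity, PPV and 1-PPV are estimated for NIR against histology (SAP 9.4), with GEE confidence intervals and raw counts.

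**The concern.** Both methods are applied to the same lesions in the same operation, so a claim that one localizes better than the other concerns both kinds of disagreement: lesions that only NIR found and lesions that only standard technique found. The primary endpoint uses the first kind and not the second. The hypothesis sentence therefore promises a conclusion that the test cannot deliver, and Protocol 10.3.1 and 10.3.2 contradict each other on whether a comparison is being made.

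What is at stake is the conclusion drawn from a positive result. If the sentence stays, 15/86 can be read as confirming superiority for localization, although the same 15/86 is compatible with NIR locating more, as many, or fewer of the preoperatively identified lesions than standard technique.

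**Working it through.** **Inputs.** From the Protocol synopsis, Statistical Methods: "assuming a 20% true rate of at least one CSE, two-sided 5% Type 1 error and 80% power" and "the sample size to rule out a CSE rate less than or equal to 10% requires 86 evaluable subjects in the primary analysis group", with success at 15/86. The documents give no rate at which NIR misses lesions that standard technique finds, so that rate is assumed below and shown over a range.

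**1. The plan's own figures.**
- Sample size by normal approximation: n = ((1.96 × √(0.10 × 0.90) + 0.8416 × √(0.20 × 0.80)) / 0.10)² = ((0.5880 + 0.3366) / 0.10)² = 85.5, rounded up to 86.
- Success rule: P(X ≥ 15 | n = 86, p = 0.10) = 0.0230, within 0.025. For 14 the probability is 0.0461, so 15 is the smallest valid count.
- Clopper-Pearson interval at 15/86: 10.1% to 27.1%, as stated.

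These reproduce, and the binomial test is valid for the question it asks. (The exact power of the 15/86 rule at 20% is 76.3%, not 80%. That is a separate matter, but the figure is used in step 4.)

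**2. What the test uses.** For preoperatively identified lesions:

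| | NIR found | NIR did not find |
|---|---|---|
| Standard found | a | c |
| Standard did not find | b | d |

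NIR locates (a + b)/n, standard technique locates (a + c)/n, and the difference is (b − c)/n. Superiority is a statement about b − c. Type A counts b only; c has no place in the endpoint, the null hypothesis or the success rule.

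**3. Illustration at the success boundary.** Assume 86 subjects with one lesion each, every lesion found by at least one method (d = 0), and all 15 events of type A (b = 15). Standard technique then finds 86 − 15 = 71, and NIR finds 86 − c.

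| c (assumed) | NIR | Standard | Difference |
|---|---|---|---|
| 5 | 81/86 = 94.2% | 71/86 = 82.6% | +10/86 = +11.6 points |
| 15 | 71/86 = 82.6% | 71/86 = 82.6% | 0 |
| 17 | 69/86 = 80.2% | 71/86 = 82.6% | −2/86 = −2.3 points |

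The primary result is 15/86 in every row. As a yardstick, the one-sided exact McNemar p-value, P(X ≥ 15 | 15 + c, 0.5), is 0.021 at c = 5 and 0.039 at c = 6. At the boundary, the paired data would favour NIR at the 0.025 level only with five or fewer NIR misses.

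**4. Range of assumed miss rates.** Take the design rate of 20% as all type A, with one lesion per subject. The exact probability of reaching 15/86 is 76.3%. The other columns come from 200,000 simulated trials per row.

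| True c | True difference | P(at least 15/86) | P(at least 15/86 and NIR observed to find fewer) | P(one-sided McNemar p ≤ 0.025) |
|---|---|---|---|---|
| 10% | +10 points | 76.3% | 0.2% | about 32% |
| 20% | 0 | 76.3% | 25% | 1.7% |
| 25% | −5 | 76.3% | 50% | 0.25% |
| 30% | −10 | 76.3% | 66% | 0.03% |
| 40% | −20 | 76.3% | 75% | about 0 |

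The chance of success does not move with c. The rows show that independence; they do not predict what c will be.

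**5. Where NIR misses do appear.** A histologic cancer that does not fluoresce in vivo is a false negative in the secondary sensitivity, TP/(TP + FN). Type A accepts any lesion other than normal lung, so the two cover different lesions: a non-cancerous lesion found by palpation and missed by NIR enters no analysis in the readable plan. No sensitivity or localization rate is planned for standard technique.

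**The case against.** The strongest reply is that this is an add-on design. NIR always follows white light and/or palpation, and both efficacy populations require that order. A lesion already found is not lost because it fails to fluoresce. Yield beyond a 10% floor is a coherent target, and Protocol 10.3.1 disclaims a treatment comparison. This stands. It means that the endpoint and the 10% test can stay, and it is also why the word superior does not fit.

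A reader might go further in four ways that the documents do not support:

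- *NIR misses are never counted.* They are, for cancer, in the in vivo sensitivity. If all 86 lesions in the illustration were cancers, 17 misses would be reported as a sensitivity of 69/86 = 80.2%. What is missing is the 71/86 beside it, and any count for non-cancerous lesions.
- *No paired comparison is planned anywhere.* The text between Protocol 2.2.2 and 2.2.4, the text between SAP 3.2 and 3.4, and the SAP table list are redacted. An exploratory paired table cannot be excluded, though it would not alter the hypothesis sentence or the success rule.
- *The trial will report superiority on 15/86.* The success rule says only that the primary endpoint is met. How the result will be described is not stated.
- *NIR is probably worse.* No miss rate is given. The tables show what is possible, not what is likely.

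**Conclusion.** The point holds as a mismatch between the stated hypothesis and the test, and as a contradiction between Protocol 10.3.1 and 10.3.2. Meeting 15/86 supports added yield, in CSEs, of NIR used after standard technique. It does not support superiority for localizing preoperatively identified lesions.

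The size can only be illustrated. With one lesion per subject, all 15 events of type A and every lesion found by at least one method, 15 or more NIR misses leave NIR no better than standard technique at 71/86. If some of the 15 events are of types B, C or D, the result says still less about localization of preoperatively identified lesions.

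It would be tempting to conclude that a paired analysis could restore the superiority claim. It could not by itself: NIR is read second, unblinded, by a surgeon who knows the result of the first search, so the paired difference carries order and knowledge bias. The validity of the binomial test and the success rule are not in question here.

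**What to change.** 1. In Protocol 10.3.2 and SAP 9.2, replace the superiority sentence with one that the test supports, for example: *VGT-309 with NIR imaging, used after white light and/or palpation, yields at least one CSE in more than 10% of subjects.* This agrees with Protocol 10.3.1. Use the same and/or wording in both documents; SAP 9.2 now has only *and*.
2. In SAP 9.3, add a descriptive paired 2×2 table for preoperatively identified lesions: standard technique found or not found, by NIR found or not found in vivo. Report both discordant counts and the paired difference in localization rate with a 95% confidence interval clustered by subject. State beside it that NIR is always read second and unblinded, so the table is descriptive and does not by itself establish superiority.

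**Cost.** A wording change in two places and one extra table. Sample size, test and success rule are unchanged. Protocol 8.3 already has lesions recorded by technique; the sponsor should confirm that the case report form links the two results lesion by lesion, since the form is not shown. The price is that the claim narrows from *superior to* to *adds to*.

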10.4 Safety Analysis

Unless otherwise specified, safety analyses will be conducted in the safety population. Safety will be evaluated by assessment of clinical laboratory tests, physical exams, ECGs and vital sign measurements at various time points during the study, and by the documentation of AEs.

10.4.1 Adverse Events

No statistical testing will be performed for safety data.

Adverse events will be summarized by the Medical Dictionary for Regulatory Activities (MedDRA) system organ class and preferred term. The MedDRA version current at the start of the study will be used throughout the study. A treatment-emergent adverse event (TEAE) is defined as any adverse event that begins on or after the date of administration of VGT-309.

An overall summary of TEAEs will be provided. The following summaries (number and percentage of subjects) of TEAEs (by System Organ Class and Preferred Term) will be provided:

- TEAEs.
- Treatment-related TEAEs.
- TEAEs leading to study drug discontinuation (infusion interruption or discontinuation)
- Serious TEAEs.
- Treatment-related Serious TEAEs.

10.4.2 Clinical Laboratory Data

Summaries of clinical laboratory results and change from baseline will be performed using descriptive statistics by scheduled visit. No statistical testing will be performed.

10.4.3 Other Safety Evaluations

Individual data for physical examination findings, clinical labs, ECGs and vital signs will be listed by subject and summarized by incidence of events/abnormalities or descriptive statistics as appropriate. Clinically Significant (CS) findings for PE, clinical labs, ECG and vital signs will be reviewed, and when appropriate, these CS findings will be reported as AEs.

11. RECORDING AND COLLECTION OF DATA

11.1 Case Report Form

The Investigator or designee will record all data collected by an Electronic Data Capture system (EDC) containing the electronic Case Report Form (eCRF) provided for that purpose. The site will be suitably trained on the use of the EDC and eCRF and appropriate site personnel will be provided electronic signatures.

All site entries will be made in a secured web site and the Principal Investigator will review the record for completeness. Upon completion of the review, the PI will sign electronically in the signature page of the eCRF.

The Investigator or designee will make necessary eCRF corrections. The Investigator must authorize the corrections to the entered data on eCRF.

Specific instructions on use of the EDC system and guidelines for data entry and correction will be provided to the sites in the Case Report Form Completion Guidelines available as part of the EDC system.

